NCT02162810

Study Title: Effect of Steroids on Post-Operative Complications Following Proximal Hypospadias Repair

Study Objective:

The primary objective of this study is to determine the efficacy of administering a short course of postoperative oral steroids in pediatric patients undergoing proximal hypospadias repair as prevention against complications. Specifically, the study aims to assess if the use of steroids i) decreases the incidence of fistula formation, glans dehiscence, wound breakdown, meatal stenosis, urethral stricture formation, or diverticula formation, and the need for subsequent redo-hypospadias surgeries and/or fistula repairs and ii) improves the quality of wound healing including the overall cosmetic appearance of the phallus (i.e. the location of the urethral meatus).

Study Design:

This is an experimental study that will be prospective, randomized, placebo-controlled, and double-blind. There will be no cross-over arm.

Primary and secondary study endpoints:

The study aims to assess if the steroids i) decrease the incidence of glans dehiscence, wound breakdown, fistula formation, meatal stenosis, urethral stricture formation, urethral diverticulum formation, meatal regression, and the need for subsequent redo-hypospadias surgeries and/or fistula repairs and ii) improve the quality of wound healing including the overall cosmetic appearance of the phallus (i.e. location of the urethral meatus)

The catheter removal visit (7-10 days after surgery) & the initial follow up visit (6-12 weeks after surgery) as well as data from 1 year postoperatively, after toilet training, and after puberty. We plan to analyze and present preliminary data when we have data on a significant cohort from the first 2-3 timepoints as it will be many years until we have the post-puberty followups since we operate on these subjects, on average, under age 2 or so.

Inclusion criteria:

All male patients' ages ranging from 3 months to 16 years seen at Department of Urology and diagnosed with hypospadias will be included in this study.

Exclusion criteria:

Patients taking steroids at the time of surgery or within six weeks of surgery
Patients with a history of steroid hypersensitivity reactions
Patients who are immunocompromised or taking immunomodulatory medications
Patients with fungal infections
Females

Selection will be based on parent willingness to allow the child to participate in the study.

Enrollment goal: 300

Recruitment methods:

The clinician will discuss the project during the routine clinical exam and provide an age appropriate explanation with the patient and the patient's parents. If the patient's parents and patient express interest in study participation, the clinician will provide the parents and patient with the IRB approved informed consent document during the subject's routine clinical exam. During the initial visit in the Urology Outpatient Clinic, the clinical diagnosis of hypospadias will be made by a physician, nurse practitioner, or a physician assistant. An initial documentation of the degree of hypospadias will be made. The patients will be scheduled to undergo surgery to repair the hypospadias when it is clinically indicated, and surgery will typically take place when the child is between 6 and 12 months of age. The age range for this study will be 3 months to 16 years to allow for collection of data during follow up visits until the subjects reach puberty. Ideally, the surgeon or a co-investigator will review the study with the parent of the patient during the child's diagnostic-surgical listing visit and, if participation is desired, the surgeon will obtain written informed consent. If the consent is not obtained at the diagnostic-surgical listing visit, a co-investigator will contact the parent by telephone 1-2 weeks prior to listed surgery to explain the study and inquire if there is interest in participation; if so, the consent form will be mailed or faxed to the parent for review. The purpose of this pre-surgery phone call is to eliminate any coercion that might play a role if the study were to be introduced to the parent on the day of the surgery alone and to give the parent time to consider the study before agreeing to participate. These patients will be identified at the existing weekly Division of Pediatric Urology Pre-Operative conference at which the surgeons/co-investigators meet to review the upcoming listed cases. A co-investigator will then meet with the interested parent on the day of the surgery to answer any questions as well as to review the study and consent form. If the parent wishes to enroll their child in the study at this point, the surgeon will obtain written and verbal consent for participation. The decision about whether or not to participate in the study will not change the type or the quality of the surgery that is performed.

Purpose, specific aims or objectives, and hypotheses to be tested:

The primary objective of this study is to determine the efficacy of administering a course of postoperative oral steroids as a preventative measure against complications/a means of enhancing repair in patients undergoing surgery for proximal hypospadias.

It is our hypothesis that a short course of postoperative steroids will facilitate healing of hypospadias to the degree that it will minimize the risk of wound complications. This hypothesis is based on the known scientific effects of corticosteroids on healing as well as the experience of the senior investigator. It is only through completion of a prospective, double-blinded, randomized, placebo-controlled study that we will be able to clearly and convincingly demonstrate that the risks of wound complications is significantly lowered with steroids to justify their routine use in this patient population.

Relevant prior experience and gaps in current knowledge. Scientific or scholarly background for, rationale for, and significance of the research based on existing literature and how it will add to existing knowledge:

Proximal hypospadias repair is a surgery for males who are born with an abnormally located urethral meatus that can be on the proximal third of the shaft of the penis, at the penoscrotal junction, in the scrotum, or on the perineum. With this procedure, a urethra is constructed and pathologic penile curvature is corrected in order to relocate the meatal opening to the glans penis. The goals of hypospadias surgery are to allow for normal function of the penis, which includes the ability to void a straight, non-obstructed urinary stream without spray or dribbling, to have a straight erection, and to propel ejaculate, with a normal penile appearance.

Unfortunately, proximal hypospadias repair has a relatively high postoperative complication rate (reports range from 12-60% with a sum 207/677 [31%] from: Aoki, 2008; Bush, 2013; Braga, 2007; Chuang, 1995; Ghanem, 2011; Gopal, 2008; Hayashi, 2007; de Mattos e Silva, 2009; Powell, 2000; Shukla, 2004; Snodgrass, 2011). The known complications include fistula formation, glans dehiscence, wound breakdown, meatal stenosis, urethral stricture formation, diverticula formation, and meatal retraction with a poor cosmetic result, and all of these require surgical treatment under general anesthesia.

As a result, past efforts have been made to determine risk factors for known complications, which has led to the identification of the meatal location as the most significant risk factor for development of a postoperative complication in primary hypospadias repair.(Bush, 2013) Regrettably, this factor is inherent to the degree of the disease that the child presents with at the time of diagnosis and thus, is not modifiable. Potentially modifiable factors such as type of suture material, suturing technique, surgeon, and use of a urethral stent have not been found to be associated with post-operative complications. Because the high risk for postoperative complications has persisted over the past decades, efforts are needed to identify novel ways in which the high complication rate and associated morbidity can be reduced.

Surgeons have been greatly interested in the effects of corticosteroids on wound healing for years as steroids have been shown to affect all major steps of the wound healing process, which is divided into 3 overlapping phases known as inflammatory, proliferative, and remodeling. In fact, it is due to a presumed attenuation of the inflammatory phase that steroids have been shown to improve the rate of healing.(Bosanquet, 2013) Nonetheless, there have been no published studies on how steroids would influence healing as related to hypospadias repair and, in turn, the associated complication rate. It is reasonable to assume that there may be some benefit from the use of corticosteroids as they are known to decrease the expression of cytokines in wounded tissue including TGF-b1, platelet-derived growth factor, tumor necrosis factor, and interleukin-1a. This action decreases the chemotactic and mitogenic stimulus for other inflammatory cells and the infiltration of polymorphonuclear leukocytes. Additionally, corticosteroids reduce mesenchymal cell expression of keratinocyte growth factor, which alters fibroblast proliferation such that application of a steroid to a wound will delay re-epithelialization,(Wang, 2013; Namkoong, 2013) and the resultant decreased type I procollagen synthesis will cause wounds to heal with reduced contraction,(Franz, 2007; Bosanquet, 2013) a desired outcome in hypospadias repair in particular given the need for tubular healing free of narrowings that can generate turbulence or wall pressure changes. While wound tensile strength has been shown to decrease in animal studies when cortisone is chronically administered at a dose of 15-40 mg/kg/day,(Wang, 2013) systemic high-dose steroids (30 mg/kg methylprednisolone, which is 5-13 times greater strength than the doses used in the animal studies) have been shown in a randomized, double-blind, placebo-controlled trial in humans not to negatively impact wound infection or dehiscence rates, more clinically relevant measures, instead benefitting patients in the postoperative period in ways such as decreasing pain.(Schulze, 1997) Additionally, a Cochrane review of 54 randomized studies of adult cardiac surgery patients found that prophylactic corticosteroids did not increase postoperative infection or impair wound healing.(Dieleman, 2011) Of note is that the beneficial findings were associated with acute as opposed to chronic steroid use.

While the long-term use of oral corticosteroids is associated with a variety of negative side effects, the pediatric asthma population is one that has demonstrated how adverse effects of oral corticosteroids “are rarely if ever associated with short courses of steroids.”(Weinberger, 1982) Because an acute course of oral systemic steroids has been so routinely used in patients under the age of 12 with asthma exacerbations (liquid prednisolone at 1-2 mg/kg/day in 1-2 divided doses for up to 10 days, although usually given for 5 days, which is at least 19 times less than the dose proven to be safe in the randomized controlled trial mentioned above) and proven to be safe, we believe that the above sum findings and the clinical observations of our senior investigator support a randomized placebo-controlled trial to evaluate whether a 5-day post-operative course of oral prednisolone at a dose of 1.5 mg/kg/day divided into two doses leads to improved outcomes in patients who have undergone surgical repair of hypospadias.

Detailed description of all research activities (including screening and follow-up procedures) that will be performed for the purpose of this research study:

Screening procedures will consist of a medical history and physical examination pre- and post-operatively that are the same as the standard exams and medical/surgical workup that any patient would receive whether or not enrolled in the study.

During the initial visit in the Urology Outpatient Clinic, the clinical diagnosis of hypospadias will be made by a physician, nurse practitioner, or a physician assistant. An initial documentation of the degree of hypospadias will be made. The patients will be scheduled to undergo surgery to repair the hypospadias when it is clinically indicated, and surgery will typically take place when the child is between 6 and 12 months of age. The age range for this study will be 3 months to 16 years to allow for collection of data during follow up visits until the subjects reach puberty. Ideally, the surgeon or a co-investigator will review the study with the parent of the patient during the child's diagnostic-surgical listing visit and, if participation is desired, the surgeon will obtain written informed consent. If the consent is not obtained at the diagnostic-surgical listing visit, a co-investigator will contact the parent by telephone 1-2 weeks prior to listed surgery to explain the study and inquire if there is interest in participation; if so, the consent form will be mailed or faxed to the parent for review. The purpose of this pre-surgery phone call is to eliminate any coercion that might play a role if the study were to be introduced to the parent on the day of the surgery alone and to give the parent time to consider the study before agreeing to participate. These patients will be identified at the existing weekly Division of Pediatric Urology Pre-Operative conference at which the surgeons/co-investigators meet to review the upcoming listed cases. A co-investigator will then meet with the interested parent on the day of the surgery to answer any questions as well as to review the study and consent form. If the parent wishes to enroll their child in the study at this point, the surgeon will obtain written and verbal consent for participation. The decision about whether or not to participate in the study will not change the type or the quality of the surgery that is performed.

During the initial visit in the Urology Outpatient Clinic, the clinical diagnosis of hypospadias will be made by a physician, nurse practitioner, or a physician assistant. An initial documentation of the degree of hypospadias will be made. The patients will be scheduled to undergo surgery to repair the hypospadias when it is clinically indicated, and surgery will typically take place when the child is between 6 and 12 months of age. The sample size for this study will be ages 3 months of age to 16 years of age to allow for collection of data during follow up visits until the subjects reach puberty. Surgical consent will be obtained by the surgeon during the Childs normal clinical visit. Likewise, the surgeon, or a co-investigator, will review the study with the parent during the child's clinic appointment and, if participation is desired after all questions have been addressed, the study consent will be obtained. The research pharmacist at Children's Hospital of Pittsburgh of UPMC , [name], will be notified for preparation of the randomization of the steroid or placebo, aided by statisticians in the Clinical and Translational Science Institute at the University of Pittsburgh, and preparation of the 5-day prednisolone or placebo, which for this study the placebo will be a simple sugar syrup for this study, to be administered.

The type of hypospadias repair will be determined by the surgeon in the operating room at the time of the surgery based on the clinical scenario. Children will be excluded if they are found upon the exam under anesthesia in the operating room at the time of surgery not to have proximal hypospadias. The final severity of the hypospadias will be documented by the surgeon based on an examination performed in the operating room under anesthesia just prior to initiation of the surgical repair. The need for short-term postoperative stenting will be decided at the time of the procedure. After the procedure, the pharmacy will deliver the medication, prednisolone versus placebo which will be blinded from the parents as well as the surgeon, to the OR and the surgeon will bring the medication to the families after surgery. At that time the parents are instructed on how to administer the steroid or placebo, twice daily for 5 days. This constitutes the focus of the study and is the only variation from standard treatment. Parents will be instructed to call for any suspected adverse reaction to the medication versus placebo and for any findings consistent with glans dehiscence, wound breakdown, fistula formation, diverticulum formation, meatal stenosis, or urethral stricture.

All patients will be seen by the surgeon in postoperative follow up in the Urology Outpatient Clinic 7-12 days after the surgery following completion of the 5-day course of prednisolone versus placebo. Stents will be removed at this time as is standard practice. The next follow up will be at 4 to 12 weeks postoperatively as is standard practice. At a minimum, participants will be asked to follow up again at 6-months postoperative, and after toilet training, and possibly one year after puberty up until 16 years of age, which does not deviate from standard practices. Each postoperative visit will include evaluation for glans dehiscence, wound breakdown, fistula formation, diverticulum formation, the presence of meatal stenosis, the presence of a urethral stricture, and the location of the urethral meatus/cosmetic appearance of the phallus in addition to the quality and progression of wound healing and the quality of the urinary stream. Any phone calls, emergency room, or office visits that take place outside of the scheduled follow-up visits will be tracked so that a phone or office interview can be arranged to make similar assessments if they are not made at the time of those encounters. Any return to the operating room for redo-hypospadias surgery as well as the intraoperative physical exam and findings will be noted. Any adverse events associated with the medication or placebo will be noted and classified in terms of severity, expectedness, and association with the medication or placebo.

Data will be stored in RedCap, a secure server with de-identified patient information that can be accessed only by investigators on the study using their individualized usernames and passwords. Data analysis will be made on at least an annual basis to allow for early termination of the study in the case that one arm is unequivocally superior or inferior.

Power analysis used and method of statistical analysis:

We will need to enroll 64 patients in the study to reject a false null hypothesis if we assume that the complication rate for proximal hypospadias surgery is 30% and that the administration of prednisolone for five-days postoperatively at a dose of 1.5 mg/kg/day divided into two doses will decrease that rate to 5%. We will need to enroll 196 patients in the study to reject a false null hypothesis if we assume that the complication rate for proximal hypospadias surgery is 25% and that the administration of prednisolone for five-days postoperatively at a dose of 1.5 mg/kg/day divided into two doses will decrease that rate to 10%. For this reason, we would like to accrue roughly 200 patients in the study, however, we will run statistical analyses at least yearly so that the study can be concluded early if indicated.

Patients will be randomized by the research pharmacist with help from the statisticians at the Clinical and Translational Science Institute (CTSI) here at the University of Pittsburgh. The research pharmacist at Children's Hospital of Pittsburgh will blind the researchers/surgeons to the identity of the oral solution (steroid versus placebo) being administered. The placebo group will serve as the study control to determine the change in complication rate achieved through the use of steroids.

Statistical Analysis Plan:

Demographic measures (median gestation, weight, follow-up in months, incidence of NICU stay, and incidence of comorbidities) will be compared between the steroid and placebo arms using appropriate statistical approach, i.e., t-tests, Fisher's Exact test, or Wilcoxon Rank-sum test.

We were unable to meet our enrollment goal sufficient to test our hypothesis for each complication (meatal retraction, meatal stenosis, glans dehiscence, skin breakdown along suture lines, urethra breakdown proximal to glans, urethrocutaneous fistula, suspected stricture, and suspected urethral diverticulum), therefore the incidence of complication overall between the steroid and placebo groups will be analyzed using Fisher's Exact Test.

Likewise, Fisher's Exact Test will be used to test the quality of wound healing, including the location of the urethral meatus (subcoronal, distal shaft, proximal shaft, penoscrotal, scrotal perineal, and other), and the improvement of chordee (resolved/ improved/ described but not documented/ no improvement/ not described) in each category (degloving, ventral, and plication).

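### As written, adverse-event recording can miss events not attributed to the study medication; wound infection is not a solicited item, and the SAP has no by-arm adverse-event table

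*Combined protocol and SAP*

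**What the plan says.** **Recording rule.** The section describing all research activities states: "Any adverse events associated with the medication or placebo will be noted and classified". The grading fields are how severe the event was, whether it was expected, and how far it is linked to the study medication. Before discharge, "Parents will be instructed to call for any suspected adverse reaction to the medication versus placebo", and also for a list of surgical findings. Nowhere does the plan ask for all adverse events whatever their perceived cause.

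**Visit checklist.** "Each postoperative visit will include evaluation for glans dehiscence, wound breakdown, fistula formation, diverticulum formation", then meatal stenosis, stricture and meatal location or cosmesis, "in addition to the quality and progression of wound healing and the quality of the urinary stream". Infection is not named.

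**Unscheduled contacts.** "Any phone calls, emergency room, or office visits that take place outside of the scheduled follow-up visits will be tracked". The stated purpose is to arrange an interview that repeats the same assessments where the contact itself did not make them.

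**Background.** Infection appears twice as reassurance: once from a randomized human trial of high-dose methylprednisolone, and once from a review of adult cardiac surgery, which found that "prophylactic corticosteroids did not increase postoperative infection or impair wound healing". The same section says that nothing has been published on steroids and healing after hypospadias repair.

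**SAP.** It compares demographics, overall complications, wound-healing quality with meatal location, and chordee. Adverse events are not mentioned.

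**Intended use.** The purpose section wants a reduction in wound complications convincing enough "to justify their routine use in this patient population". At least yearly analyses are to allow stopping if either arm is clearly better or worse.

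**The concern.** A recommendation for routine use in children typically operated on at 6 to 12 months needs benefit weighed against harm between the randomized arms. So does a decision to stop because one arm is worse. If an event enters the record only when someone links it to a five-day oral course, some harms never become data, and no later analysis can restore them. The protocol itself treats infection as a relevant safety question for steroids. It borrows the answer from other populations and does not collect infection as a defined item in its own. The SAP then gives no place where recorded adverse events would be set out by arm.

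**Working it through.** **1. The passages side by side**

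| Type of harm | Solicited at visits? | Compared by arm in the SAP? |
|---|---|---|
| Dehiscence, skin or urethral breakdown, healing quality | Yes | Yes, within overall complications and wound healing |
| Wound infection | No; may surface under breakdown, healing or an unscheduled contact | No |
| Systemic steroid effects | No; parents call if they suspect a reaction | No |
| Any other event not linked to the medication | No; seen only if it prompts a tracked contact | No |

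The recording sentence has two readings. If *associated with* means attributed to the medication, it is a filter, and the later association grade has little left to grade. If it means occurring while on the medication, all events are recorded and the grade is useful. The text does not settle this. The instruction to parents, which asks for suspected reactions, fits the first reading.

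**2. The plan's own figures**

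There is no safety figure to reproduce. The only sample sizes are 64 (30% vs 5%) and 196 (25% vs 10%), both for the complication rate. Error rates and allocation are not stated; I assume two-sided 5%, 80% power and 1:1. Then (1.960 + 0.842)² = 7.849, and the unpooled formula gives per arm:

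- 30% vs 5%: 7.849 × (0.30×0.70 + 0.05×0.95) / 0.25² = 32.3, so 33 per arm and 66 in total.
- 25% vs 10%: 7.849 × (0.25×0.75 + 0.10×0.90) / 0.15² = 96.8, so 97 per arm and 194 in total.

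The arcsine formula gives 64 and 194. Both methods come within 2 patients of the stated figures, so the trial was sized on efficacy alone.

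**3. Effect of partial recording (assumed rates)**

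The documents give no infection rate and no attribution fraction. Assume true rates of 10% (steroid) and 3% (placebo), 98 per arm (196/2), and the same fraction *f* recorded in both blinded arms. Recorded rate = *f* × true rate, so the recorded difference = *f* × 7 points. Power is for the exact two-sided Fisher test at 5%.

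| *f* | Recorded rates | Difference (points) | Power |
|---|---|---|---|
| 1.00 | 10% vs 3% | 7.0 | 41% |
| 0.90 | 9% vs 2.7% | 6.3 | 36% |
| 0.75 | 7.5% vs 2.25% | 5.25 | 27% |
| 0.50 | 5% vs 1.5% | 3.5 | 13% |

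With 10% vs 5% and 100 per arm, power is 19% at full recording, 7% at *f* = 0.50 and 1% at *f* = 0.25.

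**4. No recorded events**

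The one-sided 95% upper bound after zero events is 1 − 0.05^(1/n): 3.0% for n = 98 and 8.9% for n = 32. If only half of events were recorded, the bound of 3.0% would apply to the recorded rate, and the true rate could be about 3.0/0.5 = 6.0%.

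**5. Smaller enrolment**

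The SAP says the enrolment goal was missed, without giving the number reached. At 32 per arm, power for 10% vs 3% is 4% even with every event recorded.

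**The case against.** Several counter-arguments carry weight.

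- **The sentence grades association, so recording may be meant to be all-cause.** This stands as a possible reading. A reader might infer that unattributed events are certainly discarded; the text does not establish that. It does need rewording, because its plain sense is the filter.
- **The SAP already compares harm.** Partly true. The two-sided test of overall complications includes glans dehiscence and skin and urethral breakdown, so impaired local healing could show. Saying that the SAP has no by-arm harm comparison at all would be too strong. Infection and systemic effects remain outside it.
- **Unscheduled calls and visits are tracked whatever the reason.** True, so it would be wrong to say that events not linked to the medication leave no trace. But the tracking serves to repeat the same checklist, which lacks infection, and it misses events that prompt no contact.
- **Blinding protects the comparison.** Parents, surgeons and researchers are blinded, so a reader who inferred bias towards one arm would go beyond the documents; that would need unblinding. Equal loss in both arms still shrinks the absolute difference.
- **Short-course safety is known from childhood asthma.** The background argues this. It lowers the expected rate of systemic effects but does not address surgical wounds in this population.
- **Sample size is the real limit.** Correct for significance testing, and the fix does not change it. That is a reason to report counts and intervals rather than rely on a test.

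**Conclusion.** The point holds as a cheap improvement, not as a threat to the efficacy result. The recording rule is circular and on its plain reading can lose unattributed events. Infection is not solicited although the protocol argues from it, and the SAP omits any by-arm account of adverse events, infection or systemic effects. The likely consequence is under-ascertainment in both arms and an absolute difference pulled towards zero, which is the falsely reassuring direction for a safety question.

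The size cannot be taken from the documents. The fall from 41% to 13% rests on assumed infection rates, an assumed 50% recording fraction and 98 per arm; with 90% recorded, power falls only to 36%. The textual gap does not depend on these figures.

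**What to change.** 1. **Recording rule.** Reword it so that all adverse events from first dose to the 4 to 12 week visit are recorded regardless of perceived cause and asked about directly at the stent-removal visit. Keep association as a classification only. The endpoints section gives 6 to 12 weeks for the same visit; reconcile the two so that the window is defined.
2. **Visit form.** Add wound infection, yes or no, with a written definition.
3. **SAP.** Add one descriptive table by randomized arm: patients with any adverse event, any serious adverse event and wound infection, each with risk difference and exact 95% confidence interval. Include it in the yearly looks that remain.
4. **Patients already past these visits.** Because enrolment had already fallen short when the SAP was written, new collection may be possible only for remaining visits. For the others, tabulate by arm the events recorded and the tracked unscheduled contacts, and state the capture limit when reporting safety.

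The cost is one question and one form item at visits already scheduled, plus one table. The sample size does not change. The downside is more minor events to log.

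### Reoperation is a stated and recorded endpoint with no analysis in the SAP, and the single pooled complication test counts suspected strictures and diverticula with no confirmation rule

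*Combined protocol and SAP*

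**What the plan says.** **Endpoints.** The study objective and the section on primary and secondary endpoints both list "the need for subsequent redo-hypospadias surgeries and/or fistula repairs". Both also list stricture and diverticulum as complications that have formed.

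**Background.** The section on prior experience lists fistula, glans dehiscence, wound breakdown, meatal stenosis, stricture, diverticula and meatal retraction, and says "all of these require surgical treatment under general anesthesia". It gives a pooled rate of 207/677 (31%).

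**Data collected.** The description of research activities has stricture, diverticulum and the other complications assessed at each postoperative visit. It adds: "Any return to the operating room for redo-hypospadias surgery as well as the intraoperative physical exam and findings will be noted".

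**Sample size.** The power section assumes a fall from 30% to 5% (64 patients) or from 25% to 10% (196 patients). It does not define the complication rate or give its source.

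**SAP.** Because enrollment fell short, the separate tests of each complication are replaced by one Fisher's exact test of overall complication incidence. The list of eight complications begins with meatal retraction, meatal stenosis and glans dehiscence and continues "skin breakdown along suture lines, urethra breakdown proximal to glans, urethrocutaneous fistula, suspected stricture, and suspected urethral diverticulum". The other analyses cover baseline measures, meatal location and chordee. Reoperation does not appear.

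**The concern.** There are two separate gaps.

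First, whether fewer boys need another operation is one of the trial's stated questions, and probably its most objective outcome. The SAP followed to the letter would not report it by arm.

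Second, after the enrollment shortfall the efficacy result on complications rests on one pooled test, so the definition of an event carries much of the trial. The SAP does not say what confirms a suspected stricture or diverticulum, whether a suspicion later excluded is removed, or at what time point the count is made. If such events are common and unrelated to treatment, they occur in both arms and pull the two rates together. A null result could then reflect the event definition rather than the drug, and a positive result would not show which kind of event was prevented.

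**Working it through.** **1. Reoperation, section by section.** It is named in the study objective, named again in the endpoints section, and recorded under the research activities. The SAP has no analysis of it. No assumption is needed. One detail matters for the fix: the data-collection sentence names redo-hypospadias surgery, while the endpoint also includes fistula repair.

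**2. Suspected events.** The objective, endpoints and background speak of stricture and diverticulum formation, and the visit assessments of the presence of a stricture. The SAP list speaks of suspected ones and gives no confirmation rule.

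**3. The plan's own sample sizes.** "We will need to enroll 64 patients in the study to reject a false null hypothesis" comes with no stated alpha, sidedness, power or allocation ratio. I assume two-sided 0.05, 80% power and 1:1. The arcsine formula is n per arm = 2 × [(1.960 + 0.842)/h]², with h = 2·arcsin√p₁ − 2·arcsin√p₂.

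- 30% vs 5%: h = 0.708, n = 31.3, rounded up to 32 per arm, total 64 (stated 64).
- 25% vs 10%: h = 0.404, n = 96.3, rounded up to 97 per arm, total 194 (stated 196).

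The unpooled-variance formula gives 66 and 194. The stated sizes are therefore reproduced closely on these assumptions.

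**4. Power of the planned test.** By exact enumeration, the two-sided Fisher test has 68% power at 32 per arm (30% vs 5%) and 75% at 98 per arm (25% vs 10%).

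**5. Extra events unaffected by the drug.** Assume that 25% vs 10% describes the complications the trial was sized on, and that a share q of the remaining children in each arm also count as events. Each rate becomes p + (1 − p)q. At q = 10%, placebo is 0.25 + 0.75 × 0.10 = 32.5% and steroid is 0.10 + 0.90 × 0.10 = 19.0%.

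| q | Placebo | Steroid | Risk ratio | Fisher power, 98 per arm |
|---|---|---|---|---|
| 0 | 25.0% | 10.0% | 0.40 | 75% |
| 5% | 28.8% | 14.5% | 0.50 | 62% |
| 10% | 32.5% | 19.0% | 0.58 | 52% |
| 15% | 36.3% | 23.5% | 0.65 | 44% |

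**6. Extra events that respond in proportion.** Take q = 10% in the placebo arm and keep the risk ratio at 0.40. The rates are 32.5% and 0.40 × 32.5% = 13.0%, and Fisher power rises to 88%.

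**7. Between the two.** With q = 10% in the placebo arm and a steroid effect that cuts the extra events by a fraction c, the steroid rate is 0.10 + 0.90 × 0.10 × (1 − c). Fisher power is 52% at c = 0, 64% at c = 20%, 70% at c = 30% and 76% at c = 40%. The composite breaks even with the 75% baseline at about c = 40%.

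The values of q and c are assumptions; the documents give neither.

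**The case against.** The strongest reply is that dilution has not been shown, and several parts of it stand.

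- **The sized endpoint is not shown to be stricter.** A reader might infer that the 25% and 30% planning rates refer to complications needing surgery, because the background says so of its own list. The 207/677 is the only pooled rate given and is close to 30%. But the power section neither defines its rate nor cites that figure, the 25% has no source, and whether the pooled reports counted only confirmed or operated events cannot be seen from these documents.
- **Skin breakdown is not a new component.** A reader might infer that the SAP added it as a minor event. Wound breakdown is already in the objective, the endpoints, the background list and the visit assessments. The SAP's skin and urethral items read as a split of it.
- **A loss of power is not a fact.** It needs extra events that the drug does not affect. The protocol hypothesises that steroids reduce wound complications, and steps 6 and 7 show that the direction can reverse.
- **Omitting reoperation dilutes nothing.** It is an unanalysed endpoint, separate from the composite.
- **The power figures are illustrative.** They use 98 per arm, while the SAP says that enrollment fell short.
- **Suspected may only describe clinical assessment at a visit.** That is possible, but the SAP does not say so, and it gives no rule for a suspicion that is later excluded.

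None of this supplies an analysis of reoperation or a confirmation rule.

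**Conclusion.** Two points hold on the text alone: reoperation is a stated and recorded endpoint without an analysis, and the pooled test admits suspected strictures and diverticula without a confirmation rule. On the second, the supportable conclusion is that the comparison **may** be diluted. At 98 per arm under 25% vs 10%, Fisher power could range from 44% (15% extra events, no drug effect on them) to about 88% (10% extra events responding in proportion), against 75% with none. That range rests on assumed event rates, two-sided 0.05 and equal arms, and describes the planned size rather than the size achieved. The documents do not support saying that power has been lost, that the trial was sized on confirmed complications, or that suture-line breakdown is a new event type. The change is worth making because it answers a stated aim at little cost.

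**What to change.** Keep the planned composite and its Fisher test. Add two comparisons by arm, each with Fisher's exact test and a risk difference with 95% confidence interval, at one fixed follow-up time point named in the SAP:

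1. Any return to the operating room for redo-hypospadias surgery or fistula repair.
2. A sensitivity version of the composite in which a suspected stricture or diverticulum counts only if confirmed at a later visit or in the operating room.

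The endpoints section and the research-activities section give different later visits (1 year and 6 months), and these must be reconciled before the time point is named. State whether the two comparisons were fixed before unblinding; if not, report them as supportive. The SAP need not assert that the planning rate refers to confirmed complications, since nothing in the documents establishes that.

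The cost is a few lines of SAP text and two analyses, largely on data already recorded, plus a check that fistula repairs are captured along with redo-hypospadias surgery. The stricter outcomes will have fewer events and wider intervals.
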